7.3 Adverse Events and Serious Adverse Events

An adverse event (AE) is generally defined as any unfavorable and unintended diagnosis, symptom, sign (including an abnormal laboratory finding), syndrome or disease which either occurs during the study, having been absent at baseline, or if present at baseline, appears to worsen. Adverse events are to be recorded regardless of their relationship to the study intervention.

A serious adverse event (SAE) is generally defined as any untoward medical occurrence that results in death, is life threatening, requires inpatient hospitalization or prolongation of existing hospitalization, results in persistent or significant disability/incapacity, or is a congenital anomaly.

Adverse events (AEs) and serious adverse events (SAEs) that are unanticipated, serious, and possibly related to the study intervention will be reported to the DSMB, IRB, and NCCIH in accordance with requirements.

Unexpected fatal or life-threatening AEs related to the intervention will be reported to the NCCIH Program Officer within 7 days. Other serious and unexpected AEs related to the intervention will be reported to the NCCIH Program Official within 15 days.

Anticipated or unrelated SAEs will be handled in a less urgent manner but will be reported to the DSMB, IRB, and NCCIH in accordance with the respective requirements.

Information to be reviewed at the DSMB meetings includes recruitment, accrual and dropout statistics, number and description of any AE or SAE, comparison of AE and SAE to stop rule for determination of need for study closure, and any other additional concerns. In the annual summary, the DSMB Report will state that they have reviewed all AE and SAE reports.

During the intervention period, at each phone contact by the research staff, participants will be assessed using the CTCAE grading scale for agitation, anxiety, and skin rash.

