The accrual and enrollment duration for the entire trial is expected to be approximately 39 months. (**Table 1**) Individual participant time in the study will be approximately 13 weeks (i.e., baseline week through week 12 follow-up).

Eligible participants will be randomly assigned to either the selfadministered hypnosis intervention group or the self-administered sham white noise group. The study hypothesis will be blinded such that all participants will be told there are

Table 1

MONTHS 1-9 Training; preparation; recruitment	MONTHS 10-42 Recruitment; sessions; data collection; data entry	MONTHS 43-47 Complete Data Collection	MONTHS 48-60 Data Management; Analyses; Write- ups
Train staff, research coordinator, and research contact staff	Recruit participants	Complete study visits	Finalize data cleaning
Develop and assemble study materials, record all audio recordings	Format data files, prepare data sets, enter data	Collect Follow- Up data and complete data entry	Analyze data
Regulatory procedures to begin recruitment		Begin planning manuscripts and presentations	Prepare manuscripts and present papers/posters

two different self-administered hypnosis programs being evaluated. Both groups will meet with a research contact staff two times (consent/baseline visit and randomization/education visit) in person (or by telephone or video conference during COVID-19 restrictions) and further contact will be by phone, with approximately 10-day intervals between calls for a total five phone calls over a 6-week span (**Table 2**). One final phone call will occur at week 11 to remind participants about the 12 week data collection. The baseline appointment will include completion of all baseline questionnaires (HFRDIS, PSQI, PROMIS Emotional Distress-Anxiety, and PSS). Participants will also be provided with a hot flash daily diary (for 7 days of baseline data collection), saliva collection materials, and a

Table 2: Weekly participant contact

Baseline In- person (or telephone or video	During the week of Week 1 Call 1	Call 2	Call 3	Call 4	Call 5
conference during COVID- 19 restrictions) Research Staff Interaction followed by 7- day Hot Flash Daily Diary; then Randomization/ education visit	Research Staff Phone contact	Research Staff Phone contact	Research Staff Phone contact	Research Staff Phone contact	Research Staff Phone contact

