5.2 Handling of Study Interventions

Participants in both groups will be scheduled to receive phone calls from a research assistant approximately every 10 days, for a total of 5 phone calls during the six-week study period (see Table 2). The first phone call will be scheduled approximately 7 days after the randomization/education appointment. This call is intended to make sure the participant understands their assigned treatment. An additional phone call will be made during week 11 to remind the participant of the week 12 data collection.

All phone calls will be scripted and structured to allow research staff/participant-contact at scheduled intervals and may be as brief as a voice-mail left by the research staff providing call-back information to several minutes spent discussing general topics outlined on the Phone Call Checklist & Research Contact Staff Notes form. Research contact staff will document the calls using this form and participants will be encouraged to maintain and use the program materials; but there will be no therapeutic intervention during the call.

The delivery of the self-administered hypnosis intervention and the self-administered sham white noise hypnosis outlined in detail for both groups of the study in the Research Standardized Intervention Delivery Manual. Information regarding overall study procedures are detailed in the Manual of Procedures (MOP).

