5.4 Adherence Assessment

Adherence will be assessed through the frequency of at-home practice. Participants will complete the Self-Hypnosis Practice Log each day beginning at Week 1 and for the duration of their participation time in the study.

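### AEs are defined against baseline for the whole study, but CTCAE grading of agitation, anxiety and skin rash is specified only for calls in the 6-week intervention period, with no matching pre-treatment grade

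*Combined protocol and SAP*

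**What the plan says.** Section 7.3 defines an AE as an unfavorable event "which either occurs during the study, having been absent at baseline, or if present at baseline, appears to worsen", and adds that "Adverse events are to be recorded regardless of their relationship to the study intervention". It gives no closing date. Section 3 sets the length of participation: "Individual participant time in the study will be approximately 13 weeks (i.e., baseline week through week 12 follow-up").

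The assessment that section 7.3 specifies is tied to one part of that time: "During the intervention period, at each phone contact by the research staff, participants will be assessed using the CTCAE grading scale". The three terms graded are agitation, anxiety and skin rash. Sections 3 and 5.2 provide five calls over the six weeks, about 10 days apart, and "The first phone call will be scheduled approximately 7 days after the randomization/education appointment".

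After week 6 the one scheduled contact is described in section 5.2 as follows: "An additional phone call will be made during week 11 to remind the participant of the week 12 data collection". Sections 3, 6.2.4 and 10.1 give the same purpose. The week-12 returns listed in section 6.2.4 (diary, practice log and questionnaire booklet) include no AE item, and Table 4 in section 6.1, as it can be read, has no AE row.

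Section 7.2 is worded more widely. It has severe or acute anxiety and agitation looked for at the history intake and followed by phone, by staff in contact with participants for the whole study.

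**The concern.** The definition needs two things that the stated procedure does not supply: a baseline state for each solicited term, and a way of asking about events over the whole period. The three terms are first graded about a week after the randomization visit, when treatment has begun. If a woman reports a grade 1 finding on the first call, there is no earlier CTCAE grade to show whether it is new, worse or unchanged. PHQ-4 scores up to 8 are eligible (exclusion starts at 9 in section 4.2), so some women will enter with mild or moderate symptoms.

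At the other end, Hypothesis 2.6 tests benefit at 12 weeks, while harm is solicited, as written, only in the first six. The program anticipates practice beyond week 6: the week-4 and week-5 recordings teach self-hypnosis without recordings and its use in daily life, and practice is logged again in week 12.

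Grade and attribution feed the reporting rule in section 7.4, the withdrawal rule in 7.5 and the individual stopping rule in 8. The DSMB also compares AE rates with pre-study assumptions (section 7) and with its stop rule (section 7.3). The inputs to those decisions should be collected on a stated schedule.

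**Working it through.** **Coverage in time.** Inputs: 1 baseline week, 6 intervention weeks, follow-up to week 12 (section 3).

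- Total: 1 + 6 + 6 = 13 weeks, which reproduces the plan's figure. It is approximate, because the randomization visit may come up to 30 days after baseline data collection.
- Share of the study with specified CTCAE grading: 6 / 13 = 46%.
- Share of the post-randomization weeks: 6 / 12 = 50%, leaving 6 of 12 weeks with none specified.
- Number of specified CTCAE assessments: 0 before treatment, 5 in the intervention period, 0 in weeks 7 to 12.

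**Coverage by term.**

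| Term | Before treatment | Weeks 1–6 | Weeks 7–12 |
|---|---|---|---|
| Skin rash | Nothing described | CTCAE at calls | Nothing specified |
| Agitation | History intake, severe or acute cases only, no grade stated (7.2) | CTCAE at calls | General watch (7.2), no specified question |
| Anxiety | Same intake; PHQ-4 at screening; PROMIS Anxiety at baseline | CTCAE at calls; PROMIS at week 6 | General watch (7.2); PROMIS at week 12 |

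**Timing of the rash question.** Section 7.2 names the HRV band as the source of skin irritation. Where HRV is collected (it is optional under COVID-19 restrictions), the band is worn in the baseline week (5.1.1, 5.1.2) and again at the end of week 6 (6.2.3, Follow-up Visits).

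- First wear: the first rash question comes about 7 days after the randomization visit. If that visit is 30 days after baseline data collection, the delay is about 30 + 7 = 37 days.
- Second wear: calls every 10 days from day 7 fall on days 7, 17, 27, 37 and 47. Six weeks is day 42, so on this spacing the fifth call falls outside the intervention period. For it to fall by day 42, the average spacing would have to be no more than (42 − 7) / 4 = 8.75 days. Table 4, as extracted, appears to mark the calls in weeks 1 to 5, which would put all five before the second wear.
- On either reading, no call inside the intervention period is assured to follow the second wear.

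**Sections 7.2 and 7.3 side by side.** Section 7.2 describes observation with no stated end, covers anxiety and agitation (and distress generally), and names no grading scale. Section 7.3 names the scale and adds rash, but stops with the intervention period. A caller at week 11 could follow either.

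**The case against.** The strongest reply is that anxiety, which section 7.2 names as the main risk, is not left without a baseline. PROMIS Anxiety is scored at baseline, week 6 and week 12 in both arms, perceived stress is measured at the same times, PHQ-4 is taken at screening, and severe or acute anxiety or agitation is sought at intake. This stands in large part. A reader might infer that worsening from baseline cannot be judged at all; for anxiety that is wrong. What remains is that PROMIS is a secondary efficacy outcome. Nothing in the plan converts it to a CTCAE grade, passes it to the caller or makes a worse score an AE, and it says nothing about rash.

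Second, the call checklist, the Manual of Procedures, the Data Safety and Monitoring Plan and the week-12 booklet are not available to us, and a Table 4 mark on the later calls has lost its footnote. Section 7.2 could be read to include week 11. A reader might infer that no safety information at all will exist for weeks 7 to 12. The documents do not support that: PROMIS is collected, spontaneous reports must be recorded, and the week-11 script is unseen. They support only that no AE assessment is specified there.

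Third, the callers are unblinded, but they do not decide alone. The AE log carries PI initials, acute distress goes to the PIs, and the PIs are to be blinded. It would go too far to say that AE rates are biased; no estimate is possible. A missing baseline grade can push classification either way, and that is the most that can be said.

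Fourth, matching solicitation to the treatment period is a defensible choice in a minimal-risk trial, and section 6.2.3 (Follow-up Visits) has the materials used for six weeks. Nor is post-week-6 practice clearly continuous. Section 5.4 says "Participants will complete the Self-Hypnosis Practice Log each day beginning at Week 1 and for the duration of their participation time in the study", but sections 6.2.2.2 and 10.1 limit the log to weeks 1 to 6 and week 12, and no section states that women keep the recordings. This lowers the stakes but does not remove the mismatch with the plan's own AE definition.

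**Conclusion.** The point holds in a limited form. Section 7.3 defines AEs over the whole study relative to baseline, but specifies CTCAE grading only at intervention-period calls. There is no pre-treatment counterpart and no AE assessment specified for week 11 or week 12, which leaves 6 of 12 post-randomization weeks. The gap is fullest for skin rash, partial for agitation and smallest for anxiety. New-versus-pre-existing judgments are open to misclassification in either direction, by an amount that cannot be estimated from the documents.

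Multiplying 232 women by 6 weeks gives 1,392 person-weeks before drop-out. That is calendar time without a specified AE question, and a reader should not take it as a count of missed events.

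The conclusion assumes that the unseen call script, procedures manual and booklet add no AE questions beyond the protocol. If they do, the remedy reduces to stating this in 7.3 and adding the baseline grade. The efficacy analysis is not affected. The change should be made because it is inexpensive and the existing contacts can carry it.

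**What to change.** In section 7.3:

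- State the AE collection window.
- Grade the same three CTCAE terms, with one open question about other events, (a) before randomization, (b) at each of the five calls, and (c) at the existing week-11 call, each time covering events since the last completed contact.
- Judge new or worsened events against the grade at (a). The baseline visit is a convenient place for it under in-person and remote conduct. The first call should then ask back to that visit, so that band wear in the baseline week is covered; the start date on the AE log separates pre-treatment events.
- Add one self-report AE item to the week-12 booklet.

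Align section 7.2 with 7.3, so that both give the same period and the same terms, and add an AE row to Table 4.

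The cost is protocol and checklist wording, a few minutes at contacts that already take place, and one booklet item. AE counts may rise slightly because more is asked. No change to treatment, withdrawal or stopping rules is proposed.

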7.4 Reporting Procedures

AEs will be collected and recorded as illustrated on **Table 5**, which includes the Participant ID, a brief description of the AE, AE start date, AE type, AE intensity, study attribution of the AE, PI initials, and date initialed.

Table 5: Adverse Event Reporting Log

STUDY NAME:										
Principal Investigator: Study Coordinator: Adverse Events: None			Site:							
Participant ID	Brief Description of AE	Start Date (mm/dd/yy)	Type of AE	AE Intensity Study PI Dat Attribution Initials (mi						
			_ Expected _ Unexpected	1: Mild 2: Moderate 3: Severe 4: Life Threatening/Disabling 5: Death	Unrelated Unlikely Possible Probable Definite					
			_ Expected _ Unexpected	- 1: Mild - 2: Moderate - 3: Severe - 4: Life - Threatening/Disabling 5: Death	Unrelated Unlikely Possible Probable Definite					

Any expected or unexpected grade 3 or 4 adverse events with at least an attribution of possibly will be reported, with serious AE's reported in 24 hours to IRB and NCCIH.

7.5 Follow-up for Adverse Events

Participants experiencing a grade 3 or 4 AE that is at least possibly related will be withdrawn from the study.

7.6 Safety Monitoring

The Data Safety Monitoring Board for this study is comprised of individuals with expertise in biostatistics, clinical research, and clinical aspects of the patient population not associated directly with recruitment, consent, intervention delivery or data management, and who work independently of the Co-PIs, [name] and [name] and Co-Investigators, [name], [name], and [name] [name]. They are not part of the key personnel involved in this grant. No member of the Board will have co-published with the either of the Co-PIs within the past three years. Board members are qualified to review the patient safety data generated by this study because of their unique expertise relative to this study. The CVs of all members of the DSMB are included in the Data Safety and Monitoring Plan (DSMP) and will be updated as needed.

8. INTERVENTION DISCONTINUATION

During intervention delivery, participants will be closely monitored, and the following "stopping rule" will apply.

For an individual participant, all study procedures will be stopped if:

- the participant wishes to stop participation and/or,
- a serious and/or unexpected grade 3 (serious) or 4 (life-threatening) AE occurs with an attribution of at least possibly related.

With their permission, randomized participants will continue to be followed if the study intervention is discontinued until the end of what would have been their participation period (i.e., to the 12-week assessment). These procedures will ensure the safety of the participants.

Additionally, the study may be closed to participant enrollment based on careful consideration of adverse events or recruitment issues as determined by the DSMB. (See Section 9.4)

9. STATISTICAL CONSIDERATIONS

General Design Issues

9.1 Primary Objective

The primary objective is to fully evaluate the efficacy of the self-administered hypnosis intervention for hot flashes, with the indication that self-administered hypnosis will significantly decrease vasomotor symptoms compared to the self-administered sham white noise hypnosis group. In order to obtain an estimate of the efficacy of the self-administered hypnosis that is not positively biased, the reported hot flashes will be analyzed using intent-to-treatment analysis.

Hypothesis 1.1

Self-administered hypnosis will significantly decrease vasomotor symptoms (hot flash score of frequency and severity) compared to the self-administered sham white noise hypnosis at 6 weeks.

Outcome Measure:

Hot Flash Daily Diary

9.2 Secondary Objectives

Secondary objectives are to evaluate the efficacy of the self-administered hypnosis compared to self-administered sham white noise hypnosis for hot flash activity interference, sleep disturbance, anxiety and perception of benefit; with the expectation that there will be significant improvements among participants in the hypnosis group when compared with the self-administered sham white noise hypnosis group. Further, we will evaluate the effects of self-administered hypnosis compared to the self-administered sham white noise hypnosis control at 12 weeks. In order to obtain estimates of the efficacy of the self-administered hypnosis that is not positively biased on the secondary outcome measures, each secondary outcome measure will be analyzed using intent-to-treatment analysis

Hypothesis 2.1

Compared to self-administered sham white noise hypnosis, self-administered hypnosis will result in significant improvements in hot flash activity interference, sleep disturbance, and anxiety at 6 and 12 weeks and perception of benefit at 6 weeks.

Outcome Measures:

- Hot Flash Related Daily Interference Scale
- PROMIS Emotional Distress Anxiety Scale
- Pittsburg Sleep Quality Index
- Subject Global Impression of Change

Additionally, mediators (perceived stress, cortisol, and heart rate variability (HRV) and moderators (hypnotizability and practice adherence) of hot flash reduction will be explored to address the following hypotheses:

Hypothesis 2.2

A decrease in perceived stress will be indicated in the self-administered hypnosis group due to the intervention, which will correspond and contribute to further decrease of the hot flash score at 6 and 12 weeks.

Outcome Measure:

Perceived Stress Scale

Hypothesis 2.3

Diurnal salivary cortisol will demonstrate better circadian rhythms (steeper slopes) in those with larger hot flash reductions and in the self-administered hypnosis group compared to self-administered sham white noise hypnosis at 6 weeks.

Outcome Measure:

• Diurnal Cortisol Rhythm

Hypothesis 2.4

Self-administration of hypnosis and greater hot flash reductions will result in higher resting and 24-hour parasympathetic activity, reflected as higher HRV, compared to self-administered sham white noise hypnosis at 6 weeks.

Outcome Measure:

• Heart rate variability monitor

Hypothesis 2.5

Higher hypnotizability scores and better adherence rates will be associated with greater reductions in hot flash scores in the self-administered hypnosis group.

Outcome Measures:

- Self-Hypnosis Practice Log
- [name] Hypnotizability Scale

Hypothesis 2.6

Self-administered hypnosis will significantly decrease vasomotor symptoms (hot flash score of frequency and severity) compared to the self-administered sham white noise hypnosis at 12 weeks. Outcome Measure

• Hot Flash Daily Diary

9.3 Sample size and randomization

We estimated the required sample size for this study with an a priori power calculation. Data from our previous studies were used to inform the power calculations. [38, 39] The daily hot flash entries are aggregated every seven days to create a weekly hot flash score. As a result, there will be one hot flash score at baseline and one for each week of data collection. For Aim #1, seven hot flash scores will be used (i.e., baseline score + weekly score for weeks 1 through 6) for each group. For this aim, we will evaluate whether or not average weekly hot flash scores between groups follow the same change pattern across time. This effect is the group-by-time interaction effect. We initially considered the G*Power software, [97] but opted for the Optimal Design software [98] because it is more readily capable of providing power estimates for designs that involve multilevel data; that is, longitudinal data (e.g., repeated measures) and/or hierarchically structured (i.e., nested) data. Data from our previous studies were used to specify the relative expected amount of variability attributable to the participants, including group differences, and the relative expected amount of variability due to natural fluctuation of each person's scores over time. A secondary benefit of using a multilevel framework for estimating power in this study is that the sample size necessary for addressing the secondary objectives are built into the sample size calculation for objective 1.

Our previous studies reveal that the vast majority of the variability in hot flash scores, including changes over time, is explained by differences between people (e.g., group assignment) rather than hot flash score simply varying to any meaningful extent for any given person across weeks. Therefore, we specified, realistically, that nearly 80% of the variability in hot flash scores across time will be attributable to differences between people. In our preliminary data mean and standard deviations for hot flash score in the intervention group at baseline was 23.43 (1.02) and follow-up at week 12; 4.61 (0.56); means and standard deviations for the control arm at baseline were 22.94 (1.23) and follow-up at week 12, 19.41 (1.36). The mean reduction for hot flash score was 18.83 for the hypnosis group from baseline as compared with 3.53 in the controls (p < .0.001; 95% CI, 12.60-17.54). Clinically significant improvement is considered to be 50% reduction over baseline. [37] We expect, at minimum, a 50% reduction in hot flash scores in the self-administered hypnosis group and 25% reduction in the self-administered sham white noise hypnosis group.

Based on previous studies, the mean hot flash score for post-menopausal women selfadministering hypnosis is about 23 with standard deviation of 10.9. We simulated 10,000 data points from a normal distribution with mean of 23 and standard deviation of 7; we used a smaller standard deviation because the standard deviation from the previous pilot was based on a small sample. Next, we simulated a 50% reduction in hot flash scores for the 5,000 simulated values to mimic the expected effect self-administered hypnosis post treatment. We also simulated a 25% reduction in hot flash scores for the other 5,000 simulated values to mimic the expected effect of the selfadministered sham white noise hypnosis at the post treatment data point. The hot flash distribution for the simulated self-administered hypnosis condition at the post treatment data point had mean of 11.4 (SD=9.8) whereas the distribution for the simulated structured attention condition at post treatment had a mean of 17.2 (SD=9.9). These effects represent a strictly standardized mean difference of .41 between the self-administered hypnosis and structured attention conditions. We used the strictly standardized mean difference in lieu of the traditional standardized mean difference because it is slightly more conservative to ensure sufficient power. The strictly standardized mean difference in the reduction rates, when taking group variability into account, of 0.41 was entered into G*Power and Optimal Design software. Using a Type I error rate (α) of 5% and power of 80%, the required sample size is 190 without attrition in both power analysis programs. Because the withinbetween interaction for two time points (i.e., baseline and follow-up) is equivalent to an independent samples t test on the difference scores, Power was computed in the G*Power using the t distribution for independent samples on the difference scores. We entered the effect size of .41, Type I error rate of 5%, Power of 80%, and N2/N1 ratio of 1 (i.e., balanced design). The required sample size was 190. Power was cross-validated in the Optimal Design software using the Person Randomized Trial Design with Single Level Trials (i.e., participants are the experimental units). Using Type I error rate of 5% and effect size of .41, the required sample size was 190. Given the expected attrition rate of 18% attrition or less, the sample size required to accomplish all aims of this study is 232 participants. We should note that the framework described above for determining power generalizes to objective #2 and the moderator analysis described in objective #3. The power analysis should also be sufficient for the mediation analysis.

Treatment Assignment Procedures

Enrolled participants will be randomized to either self-administered hypnosis or self-administered sham white noise hypnosis. Randomization will be accomplished by the statistical team with the development of two case assignment spreadsheets; one for each site, thus assuring equal treatment arms by site. Randomization will be accomplished by the statistical team using stratified permuted block randomization with fixed blocks of size four. Two strata will be used: site (University of Michigan or Baylor University) and participant subgroup (post-menopausal or breast cancer). All randomization block permutations will be generated, and one permutation will be

randomly assigned to each block. Given that block size will be fixed at four, there are six permutations of randomization. One of the six permutations will be randomly to each block of participants. The randomization information will be printed on individual cards (e.g., "46BRG32: Self-Administered Hypnosis Group" or "46BRG32: Self-Administered Sham White Noise Hypnosis Group"), each of which will be placed in a brown security envelope and sealed (one card per envelope). It is expected that each site (Baylor University and University of MI) will each randomize approximately half of the participants, but each site will receive two sets of 116 envelopes – one set of 116 for each participant subgroup. It is not expected that there be an equal distribution of participants who are post-menopausal or breast cancer survivors; rather, the randomization strategy ensures an equal distribution of each subgroup into the self-administered hypnosis intervention or self-administered sham white noise hypnosis condition regardless of the proportion of each participant subgroup within site. For example, if Baylor University randomizes 100 participants who are post-menopausal and 16 who are breast cancer survivors, having two sets of 116 randomization envelopes ensures that (1) there are enough envelopes and (2) there are 50 post-menopausal and 8 breast cancer survivors in each condition. Therefore, one set of sealed envelopes for post-menopausal participants with group assignment and one set of sealed envelopes for breast cancer survivors with group assignment will be provided to both [name] team and [name] team. The case assignment spreadsheets will be kept by the statistician, and not accessible to persons who will be educating, obtaining consent from the participants, collecting data, or interacting in any other capacity which involves contact with participants, as this may possibly cause bias in the recruitment process. All participants randomized will be included in the analyses (i.e., intent-to-treat analysis).

